## 3.5. Study Measures

### 3.5.1. Data Elements

#### 3.5.1.1. Curated Data

Data abstracted for eligible patients from the unstructured data available in the Definitive Oncology Dataset by CRNs will include the following:

- Race/Ethnicity ([Table 1](#)).
- Date of initial AML diagnosis. This date defines the *index date* for the study, as referenced below in describing other study variables ([Table 1](#)).
- Documentation of de novo versus secondary AML at index date. Secondary AML is defined as development of AML after myelodysplastic syndromes (MDS), myeloproliferative neoplasms (MPN), or following exposure to chemotherapy and/or radiotherapy ([Table 2](#)):
  - If secondary AML, documentation of use of hypomethylating agents (HMA) at any point prior to initial AML diagnosis (Y/N). If yes, name of HMA agent will be documented.
- Stage at index date ([Table 2](#)).
- Comorbidities, indicated as present versus not indicated as present at index date ( $\pm 30$  days). The conditions to be assessed will include those assessed as part of the standard Charlson Comorbidity Index. These include myocardial infarction, congestive heart failure, peripheral vascular disease, cerebrovascular accident, hemiplegia, chronic obstructive pulmonary disease, ulcer disease, diabetes, renal disease, connective tissue disease such as rheumatoid arthritis or lupus, Alzheimer's or other dementia, cirrhosis or other serious liver disease, leukemia (other than AML), lymphoma, metastatic solid tumor, and Human Immunodeficiency Virus (HIV)/acquired immunodeficiency syndrome (AIDS). The Charlson Comorbidity Index will be computed ([Table 2](#)).
- ECOG performance status, if available, or indication of impaired performance status not otherwise classified as an ECOG rating, at index date ( $\pm 30$  days) ([Table 2](#)).

- First response and best overall response to treatment from the index date through the end of the first R/R-based line of therapy or the end of the record, whichever occurs first (Table 9-Table 11, Table 14-Table 15).
- Biomarker status and date of results will be recorded at index date ( $\pm 30$  days) (Table 2).

Biomarkers collected will include:

- IDH1
- IDH2
- TP53
- Intermediate Risk
  - FLT3
  - NPM1.

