## 7. RATIONALE AND BACKGROUND

Acute Myeloid Leukemia (AML) is the most common form of fast-growing blood and bone marrow cell cancer. In the United States (US) in 2019, it is estimated there will be 21,450 new cases and 10,920 deaths from AML. The average age at diagnosis is 68 years old, and the 5-year survival rate is 26.9%. About 60%-70% of adults with AML can attain a complete remission following induction therapy with cytotoxic chemotherapies to reduce leukemic cells in the blood and bone marrow. Slightly more than 25% (45% of those who attain complete remission) are expected to survive 3 or more years and may be cured. Remission rates are related to age, with the expected remission rate of more than 65% in those younger than 60 years old. Duration of remission is shorter in older patients, and increased morbidity and mortality during induction treatment are related to older age.

Historically, the number of treatments available for newly diagnosed patients with AML has been limited. However, new treatment regimens have become available recent years (including gemtuzumab ozogamicin [GO], midostaurin, glasdegib, plus low-dose cytarabine, venetoclax plus hypomethylating agents). Given the FDA label for GO, issued September 2017, it is critical to understand the recent real-world use of GO as a treatment for AML.

The present study is focused on real-world outcomes in adult patients with AML who at any point received treatment with Mylotarg, used alone or in combination with other agents. Although the present study is focused on the receipt of this agent during first- or second-line therapy, it is expected that most of the identified patients will also go on to receive subsequent treatment. The aim of this study is to describe treatment patterns and effectiveness outcomes in a sample of oncology patients treated for AML with Mylotarg through up to two additional relapsed/refractory (R/R)-based lines of therapy (through third-line therapy).

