### 9.2. Setting

#### 9.2.1. Inclusion Criteria

Patients must meet all of the following inclusion criteria to be eligible for inclusion in the study:

1. Confirmed diagnosis of AML on or after 01 December 2014 through Clinical Research Nurse (CRN) review of provider documentation of AML diagnosis in the medical record.
2. Receipt of Mylotarg at any point during first three lines of therapy following initial AML diagnosis.
3. Age  $\geq 18$  years at initial diagnosis of AML.

There are no inclusion criteria related to minimum follow-up.

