### 9.3.2. Curated Data

Data abstracted for eligible patients from the unstructured data available in the Definitive Oncology Dataset by CRNs will include the following:

- Race/Ethnicity.
- Date of initial AML diagnosis. This date defines the *index date* for the study, as referenced below in describing other study variables.
- Documentation of de novo versus secondary AML at index date. Secondary AML is defined as development of AML after myelodysplastic syndromes (MDS), myeloproliferative neoplasms (MPN), or following exposure to chemotherapy and/or radiotherapy.
  - If secondary AML, documentation of use of hypomethylating agents (HMA) at any point prior to initial AML diagnosis (Y/N). If yes, name of HMA agent will be documented.
- Stage at index date.
- Comorbidities, indicated as present versus not indicated as present at index date ( $\pm 30$  days). The conditions to be assessed will include those assessed as part of the standard Charlson Comorbidity Index. These include myocardial infarction, congestive heart failure, peripheral vascular disease, cerebrovascular accident, hemiplegia, chronic obstructive pulmonary disease, ulcer disease, diabetes, renal disease, connective tissue disease such as rheumatoid arthritis or lupus, Alzheimer's or other dementia, cirrhosis or other serious liver disease, leukemia (other than AML), lymphoma, metastatic solid tumor, and Human Immunodeficiency Virus (HIV)/acquired immunodeficiency syndrome (AIDS).

- ECOG performance status, if available or indication of impaired performance status not otherwise classified as an ECOG rating, at index date ( $\pm 30$  days).
- First response and best overall response as described in [Section 9.7.6](#) to treatment for the first qualifying Mylotarg-containing R/R-based line of therapy from the index date through the third R/R-based line of therapy or the end of the record, whichever occurs first. Date of first positive response and best overall response will be documented.
- Documentation of European LeukemiaNet (ELN) genetic risk stratification (favorable, intermediate, adverse, or undocumented), based on provider documentation, if available, closest to index date.
- Biomarker status and date of results will be recorded at index date ( $\pm 30$  days), if available in the medical record.
  - Biomarkers collected will include the following: FLT3, IDH1, IDH2, TP53, and NPM1.

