#### **9.7.6. Methods Under Objective 4**

*Objective 4: To evaluate tumor response among AML patients who received Mylotarg in a real-world setting.*

- a. First and best tumor response in the first qualifying Mylotarg-containing R/R-based line of therapy.
- b. Time to best response in the first qualifying Mylotarg-containing R/R-based line of therapy.
- c. Duration of best response in the first qualifying Mylotarg-containing R/R-based line of therapy.

Tumor response will be assessed for the first and best overall response to treatment for the first qualifying Mylotarg-containing R/R-based line of therapy during the study period. Response classifications will be made based on the treating physician's documentation of response itself, typically informed by radiological scan reports noted in the patient record. Classification is made to the following categories: complete response, partial response (PR), stable disease (SD), progressive disease (PD), and not evaluable (NE), each based on the treating physician's statements. In cases where complete response with partial hematologic recovery (CRh), complete response with incomplete hematologic recovery (CRi), and morphologic leukemia-free state (MLFS) are explicitly included in the treating physician's statements, these additional classifications will be documented. Patients for whom the record did not clearly indicate one of these classifications will be classed as NE. These patient responses will also be classified under a secondary classification as Other Favorable, or Other Unfavorable, where the record indicated the general direction of effect in order to preserve response information for each patient, even when not classifiable according to standard response categories; these responses can be assessed in descriptive analysis. The date of the best overall response for the first qualifying Mylotarg-containing R/R-based line of therapy will be collected from the index date through the end of the third R/R-based line of therapy or the end of record, whichever occurs first. Tumor responses captured are based on treating physician's assessment in the medical record. Overall response rate will be defined as a percentage of patients whose best response is either CR, CRi or MLFS, where available. Time to best response and duration of best response will be assessed using the descriptive techniques described above.

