### 3.4. Eligibility Criteria

#### 3.4.1. Inclusion Criteria

Patients must meet all of the following inclusion criteria to be eligible for inclusion in the study:

1. Confirmed diagnosis of AML on or after 01 December 2014 through Clinical Research Nurse (CRN) review of provider documentation of AML diagnosis in the medical record.
2. Receipt of Mylotarg at any point during first 3 R/R-based lines of therapy following initial AML diagnosis date occurring on or after 9/1/2017.
3. Age  $\geq 18$  years at initial diagnosis of AML.

There are no inclusion criteria related to minimum follow-up.

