A discontinuation will be defined as stopping of a particular agent for any reason, as indicated by provider documentation of “discontinuation” or “change in therapy” in the medical record, or, in the absence of provider documentation of discontinuation or change in treatment, a change in treatment with a particular agent, with no further treatment with that agent documented in structured data, or, evidence that the patient is admitted to hospice care (as the assumption is made that all systemic therapy is discontinued at that time).

For purposes of this study, first line therapy will be defined as beginning with the first regimen the patient receives after diagnosis of the disease of interest. Subsequent lines in this study will be defined as *R/R-based lines*. *R/R-based lines* are defined by the occurrence of an R/R event or a disease progression - either may be cited, in which an R/R event or disease progression must occur for a new regimen to be interpreted as a new line of therapy. In this study, **refractory** AML is defined as disease that is nonresponsive or failing to achieve at least minimal response while on therapy. **Relapsed** status is defined as the recurrence or worsening of disease following achievement of at least a minimal response. Additionally, the documentation of advancement of disease in patients after initial AML diagnosis but before initial AML treatment will be interpreted as a disease progression. R/R events and disease progression will be defined based on provider documentation, which primarily includes progress notes.

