#### 4.3.2. Time to Event Analysis

Single time to event analyses will be conducted as specified under the study objectives. CCI [REDACTED]

Real-world time to event outcomes in this study will include:

- rwEFS/rwRFS for the first 3 R/R-based lines of therapy. rwEFS will be defined as the time from the treatment initiation date (for the first agent in the first regimen in the first line of Mylotarg-containing therapy) to the date of treatment failure (TF), relapse from Complete Response (CR) or better, or death from any cause, whichever comes first. TF is defined as failure to achieve CR or better following up to 3 cycles of Mylotarg. rwRFS will be defined as the time from the treatment initiation date (for the first agent in the first regimen in the first line of therapy) to the date of a relapse event, or death from any cause, whichever comes first.
- rwOS, from the first line of therapy through the end of record or death, whichever occurs first, and
- Duration of therapy across lines of therapy from the first line of therapy through the third R/R-based line of therapy.

The time origin for analysis of rwEFS/rwRFS is the start of therapy within each specific line of therapy, and the terminal event is the earlier of an R/R event or death. The time origin for analysis of rwOS is the start of therapy within the first line of therapy, and the terminal event is death. Patients who are not indicated to be deceased at last known contact (patients who are alive, or lost to follow-up) will be censored. The time origin for analysis of duration of therapy is start of Mylotarg, and the terminal event is discontinuation of that therapy.

#### 4.3.3. Methods under Objective 1

*Objective 1: To describe the demographic and clinical characteristics as outlined in the variable list below for patients diagnosed with AML who received Mylotarg in a real-world setting.*

Descriptive analysis as detailed in [Section 4.3.1](#) will be conducted for work under this objective. Demographic characteristics that will be reported will include sex, patient age, race/ethnicity, height, weight, BMI, insurance status, and region of residence closest to the index date. Clinical characteristics that will be reported will include comorbidities and comorbidity index score, ECOG score, and disease characteristics, such as stage at index date, cytogenetic testing at index date, and whether the AML diagnosis was de novo versus secondary.

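### SAP 3.5.1.1 stops response abstraction at the first R/R-based line, although the SAP analyses response in whichever of lines 1 to 3 first contained Mylotarg

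*SAP*

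**What the plan says.** **Response, collection.** The curated-data list in SAP 3.5.1.1 gives the window as "First response and best overall response to treatment from the index date through the end of the first R/R-based line of therapy"; a record that stops sooner closes it. It names Tables 9–11 and 14–15 as the outputs. The matching item in Protocol 9.3.2 collects first and best response "to treatment for the first qualifying Mylotarg-containing R/R-based line of therapy from the index date through the third R/R-based line of therapy". For the date of best response, Protocol 9.7.6 says it "will be collected from the index date through the end of the third R/R-based line of therapy or the end of record".

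**Response, analysis.** SAP 4.3.6 assesses first and best response for each regimen in the first qualifying Mylotarg line, and says the date of best response there will be collected. SAP 3.5.2 derives time to best response and duration of response for that line, with a window ending at the third R/R-based line. Tables 9–12 have columns L1, L2 and L3. SAP 4.1 lists response among the primary endpoints.

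**Eligibility.** SAP 3.4.1 requires "Receipt of Mylotarg at any point during first 3 R/R-based lines of therapy following initial AML diagnosis date", so the first Mylotarg line may be line 1, 2 or 3.

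**Dose changes.** SAP 3.5.2 derives these only to the end of the first R/R-based line. SAP Objective 2c asks for Mylotarg dose changes in each of the first three lines, and Protocol 9.3.4 derives dose changes through the third.

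**The concern.** The collection window is narrower than the analysis it feeds. A patient first given Mylotarg in line 2 or 3 is eligible and belongs in the response analysis, yet the response to Mylotarg falls outside what SAP 3.5.1.1 tells the abstractors to record. The bullet also omits the protocol's restriction to the Mylotarg line. Taken literally, it would therefore record that patient's response to an earlier regimen without Mylotarg and not the response of interest.

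Under SAP 4.4 such a patient is not imputed but reported as not documented. SAP 4.3.6 defines the overall response rate as a percentage of patients and makes no exclusion for undocumented response, so the patient stays in the denominator as a non-responder. Time to and duration of best response (Tables 11 and 12) could not be filled for those patients. With 20–30 patients in all, a few such cases matter.

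**Working it through.** The study is descriptive and has no sample-size figure to reproduce. The check is a comparison of windows, followed by a simple count.

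**Step 1. Windows side by side.**

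| Place | Item | Ends at |
|---|---|---|
| SAP 3.5.1.1 | first and best response, abstracted | first R/R-based line |
| Protocol 9.3.2, 9.7.6 | same, for the first Mylotarg line | third R/R-based line |
| SAP 3.5.2 | time to best response, duration of response | third R/R-based line |
| SAP 4.3.6 | best-response date, first Mylotarg line | no end line stated; may be line 1, 2 or 3 by SAP 3.4.1 |
| SAP Tables 9–12 | response outputs | L1, L2, L3 columns |
| SAP 3.5.1.1 | R/R events, progressions, treatments | third R/R-based line |
| SAP 3.5.2 | dose changes, derived | first R/R-based line |
| SAP Objective 2c; Protocol 9.3.4 | dose changes | three lines |
| SAP 3.5.1.1, 3.5.1.2 | raw dose data | third R/R-based line |

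The response bullet is the outlier among the time-windowed curated items. The conflict with SAP 4.3.6 is by implication, through eligibility; the conflict with SAP 3.5.2 is explicit.

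**Step 2. Which line is the first R/R-based line?** The Table 2 footnote defines subsequent treatment as anything after the first R/R-based line, and SAP 3.5.2 describes subsequent treatment as that given after 1L. Together these equate the two. Protocol 9.2.1 ("Receipt of Mylotarg at any point during first three lines of therapy following initial AML diagnosis") becomes three R/R-based lines in SAP 3.4.1. SAP 4.3.2 counts in the same way: "Duration of therapy across lines of therapy from the first line of therapy through the third R/R-based line of therapy". The first R/R-based line is therefore best read as 1L.

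**Step 3. How many patients could be affected?** Input from the documents: N = 20–30 (SAP 3.3). The share s whose first Mylotarg line is L2 or L3 is not given, so it is assumed. Affected patients = N × s.

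| s (assumed) | N = 20 | N = 30 |
|---|---|---|
| 10% | 20 × 0.10 = 2 | 30 × 0.10 = 3 |
| 30% | 20 × 0.30 = 6 | 30 × 0.30 = 9 |
| 50% | 20 × 0.50 = 10 | 30 × 0.50 = 15 |
| 70% | 20 × 0.70 = 14 | 30 × 0.70 = 21 |

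If abstraction followed the protocol window, the count is 0. Patients whose first Mylotarg line is L1 are unaffected either way.

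**Step 4. What the tables would show.** If columns group patients by the line in which Mylotarg was first given, an unabstracted L2 or L3 column of n patients has n/n = 100% in the not evaluable/undocumented row of Tables 9 and 10, and a response rate of 0/n.

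**Step 5. Dose changes.** The raw data run through line 3, so nothing is lost; only the derivation and reporting stop early. The visible Table 4 shell has a first-line block only, while Table 5 has three.

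**The case against.** - **The SAP may depart from the protocol.** Protocol 9.7 allows this, subject to an amendment for major changes to primary endpoints. That could explain a difference between the two documents. It cannot explain the SAP disagreeing with itself.
- **The data are ordered elsewhere.** SAP 4.3.6 says the best-response date in the first Mylotarg line will be collected, and the 3.5.1.1 list only says what the data will include. A wording slip is quite possible. But the bullet states an explicit end point, and nothing says which text prevails.
- **The table columns may be template.** Tables 14 and 15 carry L1–L3 columns although their ad-hoc subset is defined by treatment in 1L. The columns are thus weak evidence alone; the conflict with SAP 3.5.2 and 4.3.6 does not depend on them.
- **The first R/R-based line might be line 2.** A reader might infer this from SAP 4.2 ("Subsequent lines in this study will be defined as" R/R-based lines) and from Protocol 7 ("through up to two additional relapsed/refractory (R/R)-based lines of therapy (through third-line therapy"). However, Protocol 7 ends the count at third-line therapy, whereas this reading would make the third R/R-based line a fourth line. The Table 2 footnote also points to 1L. Even if line 2 were meant, line 3 would still be excluded.
- **The Table 4 shell may be incomplete as read.** Its rows carry an asterisk with no footnote. This stands, so any change to that table is conditional.

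**Conclusion.** The contradiction holds and should be fixed. As written, SAP 3.5.1.1 leaves a primary endpoint unabstracted for patients first given Mylotarg in line 2 or 3: 2–21 of 20–30 patients at assumed shares of 10–70%, and none if the protocol window was used. The dose-change conflict is real but milder.

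Three stronger conclusions are not supported:

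- **That response data were lost.** Protocol 6 planned collection from March to April 2020, starting before SAP 1.0 (1 April 2020) and ending before SAP 2.0 (9 September 2020). These are planned dates, the documents do not show whether the wording was already in Version 1.0, and nothing states which window the abstractors applied.
- **That a 0/n response rate would pass as true absence of response.** The undocumented row in the same table would show 100%, so the gap would be visible.
- **That rwEFS is generally compromised.** R/R events, progressions and deaths are still captured. Only treatment failure that depends on complete-response status is exposed, and the documents give no figure for it.

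**What to change.** 1. **SAP 3.5.1.1.** Reword the bullet to cover first and best overall response for each regimen in the first qualifying Mylotarg-containing R/R-based line, with the window running from the index date to the end of the third R/R-based line or of the record. Copying Protocol 9.3.2 unchanged would not suffice: it is per line, whereas SAP Objective 4, 3.5.2 and 4.3.6 work per regimen.
2. **SAP 3.5.2.** Extend the dose-change derivation to the end of the third R/R-based line. Make Table 4 report L2 and L3 if the full shell does not already do so.
3. **Study report.** State which response window the abstractors used. If it was the narrow one, abstract the Mylotarg-line response for the affected charts, or footnote it as not collected.
4. **Optional.** Add a sentence to SAP 4.2 that 1L counts as the first R/R-based line.

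**Cost.** If abstraction followed the protocol: two SAP bullets, possibly two table blocks, one sentence in the report, and no new data. If it followed the narrow window: also re-review of the affected charts, 2–21 at the assumed shares.

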### 3.5.1.2. Extracted Data

Data extracted for eligible patients from the structured data that are available in the Definitive Oncology Dataset through SQL query will include the following:

- Insurance status (private only, public only, both, neither) (Table 1).
- State of residence (Table 1).
- Sex (Table 1).
- Height (Table 1).
- Weight at index date ( $\pm 30$  days) (Table 1).
- Date of birth (Table 1).
- Date of death (Table 8).

- Treatments, dates of treatments, dose, and schedule for all oral (if applicable), infused, or injected anti-cancer therapies from the index date through the end of the third R/R-based line of therapy or the end of the record, whichever comes first (Table 3-Table 5).

